### **Research Abstract**

### Please type your Research Abstract here:

The Research Abstract should summarize the main points of your study in one paragraph. The following guidelines may help you:

- 1. Purpose and objective (1-2 sentences)
- 2. Study activities and population group (2-4 sentences)
- 3. Data analysis and risk/safety issues (1-2 sentences)

We propose to assess the relative role of nicotine dose and route of delivery in affecting successful switching from combustible cigarettes to e-cigarettes, as well as concomitant reductions in ad libitum cigarette smoking and exposure to harmful and potentially harmful constituents of combustion. The strategy will be to assess adoption of e-cigarette use and concomitant reduction in ad libitum smoking of subjects' usual brands of cigarettes over an 8-week period, during which they will receive nicotine or non-nicotine e-cigarettes, and nicotine skin patches. The nicotine patches will not be used as a therapeutic treatment in this study, but rather as a way to manipulate the nicotine dose, while varying the rate and route of nicotine delivery. Behavioral or "habit" aspects of e-cigarette use will be controlled for by the groups receiving non-nicotine e-cigarettes. One hundred thirty daily cigarette smokers will be randomly assigned to receive 8 weeks of exposure to the following conditions (65/group):

- 1. Nicotine containing e-cigarettes + 21 mg nicotine skin patches
- 2. Zero-nicotine e-cigarettes + 21 mg nicotine skin patches

The time commitment for subjects is 8 weeks once their participation begins, plus one follow-up session at four weeks. Subjects will return every two weeks to obtain e-cigarette and patch supplies, and for outcome measures of e-cigarette and combustible cigarette use to be collected; alternatively, remote partipants will be sent supplies in two shipments and will complete study questionnaires online. Ad libitum smoking will be assessed weekly using daily diary recordings of cigarettes smoked per day as well as the objective index of expired air carbon monoxide (CO) levels measured at the study visits.

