### **Research Summary**

### State your primary study objectives

We propose to assess the relative role of nicotine dose and route of delivery in affecting successful switching from combustible cigarettes to e-cigarettes, as well as concomitant reductions in *ad libitum* cigarette smoking and exposure to harmful and potentially harmful constituents of combustion.

The strategy will be to assess adoption of e-cigarette use and concomitant reduction in *ad libitum* smoking of subjects' usual brands of cigarettes over an 8-week period, during which they will receive nicotine or non-nicotine e-cigarettes, and nicotine skin patches. The nicotine patches will not be used as a therapeutic treatment in this study, but rather as a way to manipulate the nicotine dose, while varying the rate and route of nicotine delivery. Behavioral or "habit" aspects of e-cigarette use will be controlled for by the groups receiving non-nicotine e-cigarettes.

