### **Standard Research Summary**

**Purpose of the Study** 

Objectives & hypotheses to be tested

We propose to assess the relative role of nicotine dose and route of delivery in affecting successful switching from combustible cigarettes to e-cigarettes, as well as concomitant reductions in *ad libitum* cigarette smoking and exposure to harmful and potentially harmful constituents of combustion.

The strategy will be to assess adoption of e-cigarette use and concomitant reduction in *ad libitum* smoking of subjects' usual brands of cigarettes over an 8-week period, during which they will receive nicotine or non-nicotine e-cigarettes, and nicotine or non-nicotine skin patches. The nicotine patches will not be used as a therapeutic treatment in this study, but rather as a way to manipulate the nicotine dose, while varying the rate and route of nicotine delivery. Behavioral or "habit" aspects of e-cigarette use will be controlled for by the groups receiving non-nicotine e-cigarettes.

We hypothesize that e-cigarette use will be higher, and concomitantly, combustible cigarette use will be lower, in the nicotine e-cigarette condition compared to the zero-nicotine e-cigarette condition (i.e., comparing Group 1 vs. Group 2).

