### **Background & Significance**

Should support the scientific aims of the research

Cigarette smoking remains the leading cause of preventable disease and death in developed countries, due principally to its contributions to heart disease, chronic obstructive pulmonary disease (COPD), and cancer (Lando & Wilson, 2010). The annual death toll in the U.S. from diseases caused by smoking has been increasing steadily and is estimated to be the highest ever, 540,000/year (Carter et al., 2015).

The U.S. Surgeon General's Report of 2010 (USDHHS, 2010) concluded that the combustion products of smoke, rather than nicotine, were responsible for most smoking related diseases. E-cigarettes, which deliver nicotine in the absence of combustion, have been advanced as a tobacco harm reduction strategy. Thus far, however, only a minority of smokers have adopted e-cigarettes to satisfy their nicotine dependency without concurrent use of combustible cigarettes. A number of factors may serve as barriers to the adoption of e-cigarettes, including insufficient dose of nicotine and lack of familiar sensory/habit components (e.g., aroma, "throat hit") associated with smokers' usual brands of cigarettes. The present study will examine the relative roles of nicotine dose and route of administration in affecting the ability of smokers to transfer their dependency from combustible cigarettes (CC) to e-cigarettes.

There are several reasons why administration of a given dose of nicotine by inhalation (via e-cigarettes), vs. transdermal administration (via nicotine patches) would be more reinforcing and lead to greater switching from combustible cigarettes to e-cigarettes. First, inhaled nicotine reaches the bloodstream and brain much faster than transdermal administration (Rose et al., 2010), producing immediate reinforcing

effects. Also, inhaled nicotine produces familiar respiratory tract cues that smokers find rewarding (Rose, 2006). Indeed studies have reported a greater suppression of combustible cigarette use when smokers used e-cigarettes as an alternative compared with nicotine patch (McRobbie et al., 2014).

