Although subjects receiving nicotine from e-cigarettes will no doubt receive a range of nicotine doses, depending on the extent of use, data from previous studies (Shahab et al., 2017) suggests that the mean dose is expected on average to be similar to that provided by a 21 mg/day patch (and actual mg/day, as estimated from the number of e-liquid cartridges consumed, will be a covariate in the statistical analyses.).

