Self-reported cigarettes/day recorded on diaries will also be a secondary index of cigarette consumption. The main index of e-cigarette use will be the number of cartridges consumed, based on selfreport and counts of the number of unused e-cigarette tanks returned. We hypothesize that e-cigarette use will be higher, and concomitantly, combustible cigarette use will be lower, in the nicotine e-cigarette condition compared to the zero-nicotine e-cigarette condition (i.e., comparing Group 1 vs. Group 2). This hypotheses will be evaluated using General Linear Modeling (GLM) techniques to assess the significance of the nicotine factor, using a 1-tailed alpha=0.05. A one-tailed comparison is justified given that a higher dose of nicotine in the e-cigarette would only be expected to decrease use of conventional cigarettes. Moreover, there would be no interest in pursuing the nicotine e-cigarette plus nicotine patch combination if it led to greater smoking than the placebo e-cigarette plus nicotine patch. Thus, the 5% Type I error rate can reasonably be assigned to the 1-tailed comparison. Covariates in the analysis of combustible cigarette use will include the amount of e-cigarette use, since that will affect the overall dose of nicotine received by subjects, as well as baseline combustible cigarette use, and baseline demographic and smoking history variables (the latter will also serve as covariates in the analysis of e-cigarette use as a dependent measure). We predict at least a moderate effect size (0.5) for each of the main effects, nicotine and route of administration, so that a sample size of 50 per group will yield at least 80% power to detect the hypothesized effects.

• Summarize safety concerns, and describe the methods to monitor research subjects and their data to ensure their safety, including who will monitor the data, and the frequency of such monitoring. If a data monitoring committee will be used, describe its operation, including stopping rules and frequency of review, and if it is independent of the sponsor (per 45 CFR 46.111(a) (6)).

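### The objective and the power sentence claim a separate route-of-administration effect, but the two listed arms give only one contrast, in which added nicotine and its inhaled delivery change together

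*Combined protocol and SAP*

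**What the plan says.** The Research Abstract and the Design Overview list the same two arms, with 130 smokers randomised, 65 per group. Group 1 receives nicotine e-cigarettes plus 21 mg nicotine patches. Group 2 receives zero-nicotine e-cigarettes plus the same patches.

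The primary objective is to "assess the relative role of nicotine dose and route of delivery in affecting successful switching from combustible cigarettes to e-cigarettes". The Research Abstract and Purpose of the Study repeat it. Background & Significance says the study will "examine the relative roles of nicotine dose and route of administration in affecting the ability of smokers" to move their dependence to e-cigarettes, and the Design Overview states a similar aim. The patches are described "as a way to manipulate the nicotine dose, while varying the rate and route of nicotine delivery".

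Data Analysis & Statistical Considerations gives one hypothesis (Group 1 versus Group 2) and one test (a general linear model for the nicotine factor, one-sided alpha 0.05). The power sentence then reads "We predict at least a moderate effect size (0.5) for each of the main effects, nicotine and route of administration" and attaches at least 80% power to 50 per group. The amount of e-cigarette use is a covariate in the combustible-cigarette model. Background & Significance adds that actual mg/day, "as estimated from the number of e-liquid cartridges consumed, will be a covariate in the statistical analyses".

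Other text does not fit two arms that both receive nicotine patches. Purpose of the Study mentions "nicotine or non-nicotine skin patches", and Selection of Subjects speaks of randomisation to four conditions. The Abstract says that habit aspects "will be controlled for by the groups receiving non-nicotine e-cigarettes", in the plural.

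**The concern.** To separate dose from route, a randomised design must let one vary while the other is held fixed, or at least vary them in different patterns across arms. Here the patch is the same in both arms, so it is not a randomised factor. Putting nicotine in the e-cigarette adds study nicotine and adds the inhaled route in one step. No arm delivers similar added nicotine by the other route alone.

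The primary objective and the sample-size justification both depend on this. As written, a Group 1 versus Group 2 difference could be reported as evidence on the relative roles of dose and route. A reader of the power sentence would also believe that the trial is powered for a route effect.

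**Working it through.** **1. The plan's own power figure.** Inputs from Data Analysis & Statistical Considerations: effect size 0.5 (taken here as a standardised mean difference d), one-sided alpha 0.05, 50 per group, power at least 80%. The 65 per group comes from the Design Overview.

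Normal approximation, unadjusted two-group comparison: power = Φ(d√(n/2) − 1.645).

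- n = 50: 0.5 × √25 = 2.50; 2.50 − 1.645 = 0.855; power 0.804. The noncentral t gives 0.799.
- n = 65: 0.5 × √32.5 = 2.850; 2.850 − 1.645 = 1.205; power 0.886. The noncentral t gives 0.883.
- Required n per group for 80%: 2 × (1.645 + 0.842)² / 0.5² = 49.5, rounded up to 50.

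The plan's 50 per group and 80% therefore reproduce as one comparison of two groups.

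**2. What the two arms can estimate.** Code each arm by intercept, added study nicotine and inhaled study nicotine.

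| Arm | Patch | Intercept | Added study nicotine | Inhaled study nicotine |
|---|---|---|---|---|
| Group 1 | 21 mg | 1 | 1 | 1 |
| Group 2 | 21 mg | 1 | 0 | 0 |

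The last two columns are identical. The matrix has rank 2 for three terms, whatever the number per arm, so the assigned arms give one contrast and its effect cannot be divided between dose and route. No sample size gives power for a separate route effect here, because no contrast isolates it.

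**3. Whether the planned covariate changes this.** A person-level measure of cartridges or mg/day varies between people, so adding it makes the matrix full rank. It does not supply a randomised route comparison, for three reasons:

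- it is measured after randomisation and can be affected by the assigned arm;
- e-cigarette use is itself one of the two primary outcomes;
- inhaled study nicotine is zero by design throughout Group 2, so no one there shows what inhaled dosing does.

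The urinary nicotine equivalents listed under Sessions would describe total intake, but a value taken on treatment is also post-randomisation and has the same limit.

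**4. The text on the number and content of arms.**

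| Section | What it implies |
|---|---|
| Research Abstract; Design Overview | Two arms, 65 each, nicotine patches in both |
| Purpose of the Study and Data Analysis, hypothesis | Group 1 versus Group 2 |
| Research Abstract; primary objectives, patch phrase | Nicotine patches only |
| Purpose of the Study, patch phrase | Some patches without nicotine |
| Selection of Subjects | Four conditions |

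**The case against.** The best defence is that the only hypothesis and the only test in the plan are Group 1 versus Group 2. That contrast is estimable and its power arithmetic is right. The analysis section also gives a practical question: whether the nicotine e-cigarette plus patch is worth pursuing against the placebo e-cigarette plus patch. Answering it needs no separation of dose from route. All of this stands. But the primary objective and the power sentence then promise something that the hypothesis does not.

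A second defence is that calling study dose assigned is loose. The nicotine content of the e-cigarette is assigned; the amount taken is up to the participant, and Background & Significance expects a range. Both arms also smoke freely, so total nicotine intake may differ by less than the assigned products suggest. This is correct, and it limits what may be said about dose. It does not create a route contrast.

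A third defence is that the four conditions, the non-nicotine patches and the plural groups are leftover wording. That is plausible, although the documents do not say so. The patch phrase occurs once; the parallel sentences in the Research Abstract and the primary objectives mention only nicotine patches. A reader might infer that a four-arm trial with placebo patches is actually planned. The arm lists, the total of 130 at 65 per group and the stated hypothesis all point to two arms, so these phrases need only be reconciled.

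A reader might also infer that, with mg/day in the model, its slope comes from Group 1 alone and the arm term is a pure extrapolation of Group 1 to zero dose. The planned model does not support that. It also includes baseline cigarette use, demographics and smoking history, fitted across both groups, so Group 2 influences every coefficient. The conclusion here does not depend on that reading.

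**Conclusion.** The objective and the power sentence are wrong as written. They attribute to the design a separate route effect that two arms, both assigned 21 mg patches, cannot provide: one randomised contrast, rank 2 for three terms, and no route test described. This rests on the two-arm list being the current design and needs no numerical assumption.

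The defect goes no further. A reader might infer that the trial cannot test its hypothesis or is underpowered. The documents do not support either: for the single contrast, power is about 80% with 50 analysed per group and about 88% with 65, assuming d = 0.5, one-sided 0.05 and no covariate adjustment. Nor is 50 against 65 an error; the plan does not explain the gap, and it may allow for dropout.

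The power figures are for an unadjusted comparison. They are a reasonable guide for the e-cigarette-use outcome, whose model takes only baseline covariates. They do not describe a carbon monoxide model adjusted for e-cigarette use. Whether that adjustment belongs in the model is a separate question, not settled here.

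**What to change.** If the two listed arms stand:

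1. In the Research Abstract, primary study objectives, Purpose of the Study, Background & Significance and Design Overview, restate the aim as the effect of nicotine versus zero-nicotine e-cigarettes in smokers all assigned 21 mg patches. State that dose and route cannot be separated in this design.
2. In Data Analysis & Statistical Considerations, delete route of administration from the power sentence. Tie the power to the Group 1 versus Group 2 contrast and label it as an unadjusted two-group comparison (d = 0.5, one-sided 0.05): about 80% with 50 analysed per group, about 88% with 65. The sponsor may add whether the difference between 50 and 65 allows for dropout.
3. Reconcile with the two-arm design: the four conditions in Selection of Subjects, the non-nicotine patches in Purpose of the Study, and the sentence on patches varying the route together with the plural groups (Research Abstract, primary objectives, Purpose of the Study).

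The cost is protocol wording in those seven sections. The claim becomes narrower. Arms, enrolment and the stated test do not change. If the sponsor means to keep the route question, the protocol would have to describe arms that identify it, which is a design change and not a wording change.

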### Data Safety Monitoring Plan (DSMP)

To address potential safety issues in addition to collection of the primary study outcomes, severe side effects and adverse events potentially associated with the study will be examined, recorded and then reported to the IRB in a manner consistent with Duke HRPP policies. The principal investigator will be responsible for monitoring data collection and safety of this study.

Data collection for this study will be carried out at the Durham clinical site of the Duke Center for Smoking Cessation (CSC) or remotely via REDCap and phone contact. All members of the study team will complete research integrity ("code of conduct") and CITI (Collaborative Institutional Training Initiative) Human Research Curriculum and clinical laboratory safety training as required by Duke University Medical Center. All study staff who are involved in data collection, management, and processing will be thoroughly trained following standards of procedures prior to working on this project.

Study staff responsible for data collection will use a checklist for completion for each study visit of each participant. Missing Data Forms, along with explanations should missing data occur, will be completed by the study staff for each study visit/e-visit.

Microsoft Access will be used for logging subject information (Enrollment Log, Visit Log, etc.). Data will be entered by the study staff. The key study personnel will further examine the computerized data entries and original records for accuracy and completion.

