Subjects will be monitored throughout the duration of the study for side effects and severe adverse effects (SAEs). They will be instructed to report any side effects to the study technicians, who will communicate these reports immediately to the medical staff. The most appropriate course of action will be determined,

which may include options for dose reduction or termination of study intervention. Participants will be reminded that they have the option to withdraw from the study at any time. Subjects will also be given the 24-hour emergency contact numbers in the event that side effects or adverse events occur between sessions. SAEs will be reported to the IRB and will be monitored until resolution or stabilization.

The sponsor for this study will ensure the investigational tobacco product is distributed only to qualified members of key personnel in accordance with this protocol.

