### Emergency Unblinding

This is a blinded protocol such that all participants and all study personnel except for the Clinical Research Coordinator and the Research Program Leader are blinded to group allocation. During specific circumstances it will be necessary to unblind other study personnel, such as study team medical personnel. Emergency unblinding will occur under the discretion of the study physician (or one of the study physician assistants) in any situation in which unblinding is deemed necessary to ensure or promote the safety of a study participant. The decision to unblind for safety reasons may occur for a number of reasons and it is not possible to enumerate all potential circumstances. Examples of reasons for unblinding to ensure participant safety include situations in which it is necessary to know which study drugs the subject was taking in order to manage the side effect(s), advise the subject on the risk of future negative drug reactions, uncover potential safety information about the drug, and/or determine whether the adverse event is study related. In those situations, the Clinical Research Coordinator or Research Program Leader will inform the study physician (or physician assistant handling the event) of that subject's study condition. If unblinding occurs, that subject's data will be censored and will not be included in final data analyses.

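### Recording of adverse events is conditional on severity or suspected relation, and relatedness may be judged after the arm is revealed with no blinded entry first

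*Combined protocol and SAP*

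**What the plan says.** Four parts of the combined protocol and SAP bear on this.

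- **Data Safety Monitoring Plan (DSMP).** It commits that "severe side effects and adverse events potentially associated with the study will be examined, recorded and then reported to the IRB", following the institution's human research protection policies. Oversight is assigned in one sentence: "The principal investigator will be responsible for monitoring data collection and safety of this study". There is no grading scale, causality procedure or definition of a serious event.
- **Emergency Unblinding.** By default "all participants and all study personnel except for the Clinical Research Coordinator and the Research Program Leader are blinded to group allocation". A physician or physician assistant may break the blind "in any situation in which unblinding is deemed necessary to ensure or promote the safety of a study participant", and the examples include the need to "uncover potential safety information about the drug, and/or determine whether the adverse event is study related". The section ends: "If unblinding occurs, that subject's data will be censored and will not be included in final data analyses".
- **Risk/Benefit Assessment.** "Subjects will be monitored throughout the duration of the study for side effects and severe adverse effects (SAEs", with participants told to report any side effect to technicians, who pass it to medical staff at once. Then: "SAEs will be reported to the IRB and will be monitored until resolution or stabilization". No relatedness condition is attached.
- **Remote Study Participation.** A Side Effects Form is completed at each milestone, and the medical provider reviews all side-effect reports. The e-visits use the same questionnaires as the in-person visits, so the form appears to apply to both modes.

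**The concern.** Relatedness is normally an attribute of an event already on record. Here it helps decide whether the event goes on record, and the person deciding may know the arm. Someone who has just learned that a participant has zero-nicotine pods may be readier to call an event unrelated than someone who has learned the opposite. The DSMP record and the reports to the IRB could then differ between arms for reasons unrelated to the products.

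The exclusion rule adds a second route. If it covers safety data, the participants whose events were worrying enough to break the blind are the ones who disappear from the safety summary.

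This matters because one arm adds a nicotine e-cigarette to a 21 mg patch and continued smoking, and the Risk/Benefit Assessment itself discusses a respiratory syndrome associated with e-cigarette use.

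**Working it through.** The plan states no figure on this point, so the first check is textual.

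**Step 1: what the DSMP sentence covers.** The closing qualifier about a possible link to the study can attach to adverse events only (reading A) or to severe side effects as well (reading B). In both, *severe* is taken to apply to side effects only.

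| Event | Reading A | Reading B |
|---|---|---|
| Severe, possibly related | recorded | recorded |
| Severe, judged unrelated | recorded | not covered |
| Non-severe, possibly related | recorded | recorded |
| Non-severe, judged unrelated | not covered | not covered |

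The last row is outside the commitment on both readings.

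**Step 2: against the Risk/Benefit Assessment.** That section sends SAEs, spelled out there as severe effects, to the IRB without a relatedness condition. Under A the DSMP also sends severe events unconditionally, and it adds non-severe related ones. Under B it is narrower for severe events judged unrelated. The terms also differ: side effects, adverse events and severe adverse effects are used without definitions. Neither section separates intensity (severe) from outcome (serious), so an event of moderate intensity that leads to hospital care is not clearly placed.

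**Step 3: timing of the relatedness call.** Medical staff are blinded by default. No section requires severity or relatedness to be entered before the code is broken.

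**Step 4: illustration of direction.** From the documents: 65 per arm (Design Overview). Everything else is assumed: an equal true event risk *p* in both arms; a share *u* of events unblinded before the call; and a probability of being recorded of 0.7 if judged blind, 0.9 if unblinded to nicotine and 0.5 if unblinded to zero nicotine.

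*Unblinded participants kept.* Recorded events = 65 × p × [(1 − u) × 0.7 + u × r], with r = 0.9 or 0.5. At p = 20%, 65 × 0.2 = 13:

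| u | Nicotine | Zero nicotine | Ratio |
|---|---|---|---|
| 0 | 13 × 0.70 = 9.1 | 13 × 0.70 = 9.1 | 1.00 |
| 10% | 13 × 0.72 = 9.4 | 13 × 0.68 = 8.8 | 1.06 |
| 25% | 13 × 0.75 = 9.8 | 13 × 0.65 = 8.4 | 1.15 |
| 50% | 13 × 0.80 = 10.4 | 13 × 0.60 = 7.8 | 1.33 |

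The ratio does not depend on *p*. With a milder spread (0.9 against 0.7, blind 0.8) and u = 25%, it is 0.825 / 0.775 = 1.06.

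*Unblinded participants dropped, as Emergency Unblinding says.* Recorded proportion = p(1 − u) × 0.7 / (1 − pu). At p = 20%:

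| u, nicotine / zero | Nicotine | Zero nicotine | Ratio |
|---|---|---|---|
| 10% / 10% | 0.126 / 0.98 = 0.129 | 0.129 | 1.00 |
| 25% / 5% | 0.105 / 0.95 = 0.111 | 0.133 / 0.99 = 0.134 | 0.82 |
| 50% / 10% | 0.070 / 0.90 = 0.078 | 0.126 / 0.98 = 0.129 | 0.60 |

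For p from 10% to 40%, the last two rows give 0.81 to 0.86 and 0.58 to 0.67.

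The filter creates no arm difference in this model while the blind holds. Once the blind is broken, the direction depends on whether those participants are kept or dropped.

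**The case against.** The strongest reply has five parts.

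- **Exclusion.** Unblinded participants leave the final analyses, so a relatedness call made with the arm known would not enter them. This stands. It moves the problem to the DSMP record, the IRB reports and the loss of those participants, but does not remove it.
- **Low threshold.** An event doubtful enough to justify breaking the blind is already possibly related and already being examined. This has force. Even so, the text does not say that the event stays on record if the unblinded answer is that it is unrelated.
- **Design.** Both arms wear nicotine patches and inhale aerosol, and the Risk/Benefit Assessment attributes expected irritation to propylene glycol as well as nicotine. Learning the arm therefore gives limited grounds for calling an event unrelated, and the assumed 0.9 against 0.5 may be too wide.
- **Other capture.** Symptoms are solicited on a scheduled form and reviewed with no severity or relatedness filter. This stands: a reader might infer that unrelated complaints are lost altogether, and the documents do not support that. They do not say, however, how a complaint becomes a graded adverse event.
- **Institutional policy.** Definitions of seriousness and reportability may sit in the policies that the DSMP invokes. They are not in the documents, so this cannot be settled. The protocol still states its own scope for recording.

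A reader might also infer that the DSMP contradicts the Risk/Benefit Assessment. That needs reading B. Under A both send severe events to the IRB, and what remains is a mismatch of terms and scope.

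**Conclusion.** The point holds in a limited form. The DSMP makes severity or suspected relation a condition for recording, Emergency Unblinding allows relatedness to be settled with the arm known, and no blinded entry is required first. The risk falls on the adverse-event record and IRB reports, and on the loss of participants whose events prompted unblinding.

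The adverse-event record does not affect the primary test: in Data Analysis & Statistical Considerations adverse events are neither an outcome nor a covariate, and no comparison of events by arm is planned.

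A reader might take the ratios above as an estimate of bias in the nicotine arm's event rate. They are not. Every probability is assumed, the ratios fall on both sides of 1.00, and the documents give no event rate, unblinding rate or relatedness rate from which an arm ratio could be derived. They show only that the distortion is possible and that its direction is not fixed. Unblinding is also meant to be an emergency exception, which favours the small end.

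**What to change.** - **DSMP.** State that every reported adverse event is recorded whatever its severity or suspected relation, with intensity, seriousness and relatedness as separate graded attributes. Say how entries on the Side Effects Form pass into that record.
- **DSMP and Risk/Benefit Assessment.** Use one set of defined terms and one statement of which events go to the IRB.
- **Emergency Unblinding.** Have a blinded provider record severity and relatedness before the code is broken whenever this does not delay emergency unblinding, and use that entry in safety summaries. Limit the exclusion rule so that unblinded participants' safety data are kept. The clinician's discretion to unblind is unchanged.

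The cost is wording in three sections and a little more event logging for 130 participants.
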